Medication Adherence: We will assess adherence to the Target Medication with Medication Event Monitoring System (MEMS). MEMS are electronic monitoring caps that electronically record the date and time of medication bottle openings. Research studies indicate that MEMS use does not influence adherence. Because MEMS caps are costly, we will measure adherence to one oral hypoglycemic medication, which participants will identify as the one they are prescribed at the highest dosing frequency. We will also ask participants to keep a MEMS log to report unintended or missed openings (e.g. early pill removal to be taken later in the day) or prolonged non-usage (e.g., if hospitalized). MEMS adherence to a single medication correlates highly with adherence to other medications. For randomized participants, we will download MEMS data every month for 12 months. Prior to each monthly MEMS data download visit, the study coordinator will logon to EMR to see if the participant’s Target Medication dose was changed. If she detects a medication change, she will ask the RA to visit the participant at home to ensure that he/she makes the appropriate adjustment. For example, if the MEMS-monitored drug is discontinued, the RA will ensure that the newly prescribed drug is placed in the MEMS bottle. We will also ask participants to call the study coordinator if the PCP makes any medication changes.

We will assess self-reported adherence with the Morisky Medication Adherence Scale (MMAS). The MMAS is a widely used, validated self-report medication adherence instrument. Scores range from 0 to 4, with higher scores indicating better adherence. In adults with DM (37% AA), Morisky scores ≥ 3 were associated with a 10% lower HbA1c level. Although self-reports often overestimate actual adherence and are biased by memory problems, self-reports are commonly used in clinical practice and will provide a useful comparison to MEMS data.

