We will also assess Pharmacy Refill Prescription Data. At 3, 6, 9, and 12 months, we will fax a release form (signed by the participant) to the pharmacy(cies) where s/he obtained their medications. The release will ask the pharmacist(s) to fax a printout of all medication fills over the study period to the Study Coordinator. These are available as standardized reports in pharmacy computer systems. The reports show the medication name, dose, frequency, quantity, and date filled. Our experience obtaining medication labels for MEMS bottles during our pilot study suggests that pharmacies will cooperate with this data request. Our team pharmacist ([name]) will identify all oral DM medications and calculate the Proportion of Days Covered (PDC), an established measure of prescription-based adherence developed by the Pharmacy Quality Alliance and endorsed for DM medications by the National Quality Forum. We will define PDC-adherence as having adequate supply of hypoglycemic medication for $\geq 80\%$ of days from baseline to 6 months, and from 6 to 12 months.

Health Care Utilization: The Study Coordinator will review the EMR every 6 months to record incident medical events and track number of physician visits, screening eye and foot examinations, acute hospitalizations, ER visits, and deaths. We will specifically look for medical events due to adverse drug reactions. We will also record any changes to the diabetes medication regimen. We will supplement these data by asking participants if they received any medical care outside of the TJU health system.

Social Supports: We will assess receipt of tangible assistance with medications and other daily living activities when we complete the Activities of Daily Living–Prevention Instrument. Asking participants if someone helps them with each activity will identify different sources of support for different tasks. This will yield several quantitative measures of tangible assistance including number and relation of different helpers (e.g. family vs. friends vs. paid assistants); number and nature of tasks for which assistance is routinely provided, and unmet needs (i. e., tasks for which assistance is needed but none is routinely available).

Table 2. Conceptualization of Study Measures

Variable	Name of Measure	Occasion
Primary Outcome:		
Glycemic Control	Hemoglobin A1c	Baseline, 6, 12
Secondary Outcomes:		

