1. PC-OT Collaboration: The OT and the PCP will have a minimum of 4 EMR communications. They begin by reviewing a participant's medications and when they should be taken, identify evidence of polypharmacy, and discuss a participant's target HbA1c, given his/her current HbA1c ≥ 7.5 and $\leq 80\%$ adherence. The PCP will decide if: 1) the OT will increase adherence to the current regimen (likely if the participant takes metformin); or 2) the PCP will change the regimen (e.g., reduce sulfonylurea dose) to avoid hypoglycemia, anticipating that better adherence will lower blood glucose. The PCP will also inform the OT of relevant medical factors (e.g., comorbidities, exercise limitations) that may influence DSM. The OT will then begin in-home evaluation and treatment. After the 3rd session, the OT will inform the PCP via the EMR of the medication adherence Action Plans (e.g., linking medication-taking to morning routines, organizing medications), and convey any question a participant has about their medications (e.g., possible side effects). The PCP will respond, approve, or modify the plan via the EMR. In subsequent contacts, the OT and PCP will discuss treatment progress and Action Plans to improve diet and exercise. The PCP will reinforce Action Plans with participants during office visits (about every 3 months). The OT will update the PCP after the 5th session, and after each of the 3 booster sessions. The OT will inform the PCP of clinical (e.g., persistent depression) or treatment information (needs prescription refill). The PCP will respond and post incident health events and needed health screens for the OT to include in future Action Plans

2. DM Education: The OT will provide DM education throughout the intervention to build knowledge and skills (e.g., blood sugar monitoring) according to national standards. The OT will review the NIH publication, *"4 Steps to Control your Diabetes for Life"* and *"Project DECIDE"* (Decision-making Education for Choices In Diabetes Everyday) educational materials. Previous studies have demonstrated the value of the latter materials in older AAs with DM and cognitive impairment. The OTs will tailor the education to participants' cognitive strengths and deficits. They will respect participants' learning pace as they introduce new information and use repetition and "reflecting back" (i.e., asking participants to state what they understand in their own words) to ensure adequate understanding.

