b) Other DSM Practices: In subsequent sessions the OT develops BA Action Plans to improve other DSM practices. Action Plans for diet might include reducing soft drink consumption, eating 3 vegetables/day, eliminating table salt, reading food labels, and using the plate method to balance food portion by food group. For exercise, Action Plans might include using a pedometer to monitor/increase physical activity, doing chair exercises 3 times/day, walking to church). Glucose monitoring plans might include finger sticks linked to meals, or keeping glucose tablets in purse to treat hypoglycemia. The OT will provide skills training as needed (e.g., using a glucometer, plate method to organize meals).

5. Booster Sessions (Months 6, 8, and 10): Scheduling booster sessions will sustain the therapeutic relationship and treatment gains and reduce attrition. The OT will administer 3 in-home booster sessions to reinforce medication adherence and other DSM activities. Prior to each session, the OT will review the EMR to identify changes in a participant's health or medications. If a participant starts insulin, the OT will address that in the treatment plan. The OT and participant will review Action Plans from previous sessions, identify obstacles, and modify Action Plans to accommodate changes in cognition, health, medications, or social circumstances. The OT also provides information on resources to address future needs.

Enhanced Usual Care (EUC):

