The control treatment is EUC, which is comprised of "Usual Care" (i.e., routine PCP-delivered medical care) that is "Enhanced" with in-home, low-intensity education and support delivered by a bachelor's level Community Health Worker (CHW). The education component aims to increase DM knowledge and controls for the nonspecific effects of the in-home OT visits. Similar interventions, delivered by lay educators, lead to modest increases in glycemic control in ethnic minorities and are congruent with the American Association of Diabetes Educators' position statement on the role of CHWs in community care of persons with DM. In this RCT, EUC exceeds usual care in its individual attention to participants and use of DM educational materials specifically designed for older AAs with cognitive impairment. The CHWs will meet with participants in their homes at the same frequency and intensity (including booster sessions) and use the same educational materials as the OTs but the CHWs will not interact with PCPs, access the EMR, or develop Action Plans to increase medication adherence or other DSM practices. During each treatment session, the CHW will review core aspects of DM using the written materials to structure the sessions. The CHWs will also facilitate participants' personal expression about the impact of memory loss, DM, and aging on their lives.

CHAPTER 9. ADVERSE EVENTS AND ALERTS

1. Serious adverse events

In providing oversight to human subject safety we distinguish between an Alert and a Serious Adverse Event. We consider an Alert to be a dangerous situation discovered to exist by a member of the research team that is not related to the conduct of the research study. Alerts are not specific to or consequences of the study but represent situations that may be encountered in any interaction with a participant in a home. An example of an Alert may be a hazardous home condition (e.g., no fan or air conditioning and windows unable to open in summer where the home reaches temperatures over 100 degrees).

As per the IRB at TJU, we will report Serious Adverse Events (SAE) (study related or otherwise) to the IRB within 48 hours of learning of an event. Examples of SAEs include in-patient hospitalization, emergency room visits, or any other event that significantly impacts a patient's health status.

2. Documentation

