For an alert, documentation involves notifying designated members of the research team (PI and project director) and completing an Alert Event Reporting Form within 24 hours of occurrence of the event. The reporting of alerts to the IRB of TJU is not required.

For a serious adverse event, documentation involves notifying the PI and project director immediately, completing the TJU IRB Serious Adverse Event form, and notifying the TJU IRB within 48 hours of occurrence. Although this is a minimal risk study, all study personal will be trained in these alert and serious adverse event procedures.

The PI will be informed of alerts, actions taken, and resolution. For a serious adverse event, the PI will be notified as soon as the event occurs, either by telephone from the participant's home or immediately there after.

CHAPTER 10: DATA MANAGEMENT

1. General issues

All assessment forms will be created in Teleform, which is a tool whereby data collected in the field are entered directly into a computer. This will be accomplished as follows. The OA will take a laptop computer to all in-home assessments. The computer will prompt the OA to ask each question and enter the participant's response directly into the computer. Immediately after the assessment, the OA will back up the completed assessment on a memory stick. Weekly, the OA will meet with the project director to turn over electronic copies of assessments that were completed the previous week. The electronic copy will be stored on the project director's hard drive, and added to the ongoing database of all participants' completed assessments. The advantages of this method are: (1) it eliminates the need for a data entry person; (2) that skip patterns are built into the program, minimizing this type of data entry error; and (3) the computer signals the OA when questions are skipped or out-of-range values are entered. The OA will bring a back-up computer battery to all assessments. Further, the OA will also bring a blank hard copy of the assessment should the computer malfunction. All computers used for data collection and storage will be encrypted and password protected. The following data will be collected with written forms which will be entered by hand: (1) intervention notes; (2) intervention forms; and (3) data collected from the EMR.

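### Hypoglycaemia is anticipated but not named as a data item, event capture may be fuller in PC-OT than in EUC, and the two SAE reporting clocks contradict each other

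*Combined protocol and SAP*

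**What the plan says.** **Anticipated harm.** Chapter 8 (PC-OT, item 1) lets the PCP alter the regimen "to avoid hypoglycemia, anticipating that better adherence will lower blood glucose". Item 4b gives, as an example Action Plan, "keeping glucose tablets in purse to treat hypoglycemia".

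**Where events are sought.** Chapter 5, section 2 (Health Care Utilization) states: "The Study Coordinator will review the EMR every 6 months to record incident medical events". On drug harms it adds: "We will specifically look for medical events due to adverse drug reactions". It then says: "We will supplement these data by asking participants if they received any medical care outside of the TJU health system". Table 2 lists the EMR and participant report as sources for interim medical events at baseline and months 6 and 12.

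**Who looks.** Chapter 6, section 1 puts the study coordinator among the staff who know the assignment. The research assistant is not on that list.

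**Monthly contact.** Chapter 5 (Medication Adherence) says: "For randomized participants, we will download MEMS data every month for 12 months". Chapter 4 has the research assistant make these home visits in both arms.

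**SAE reporting.** Chapter 9, section 1 counts hospital admissions and ER visits as SAEs and requires a report to the IRB "within 48 hours of learning of an event". Section 2 of the same chapter requires "notifying the TJU IRB within 48 hours of occurrence".

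**The concern.** PC-OT is meant to increase the intake of glucose-lowering drugs in older people with mild cognitive impairment. The plan itself links better adherence to lower glucose and to hypoglycaemia. If that event is never asked about by name, the trial could report an HbA1c benefit with no usable figure for a harm it foresaw.

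The comparison between arms is also exposed. The record from which events are extracted is one that the intervention writes into, in one arm only, and the person extracting them is unmasked. ER visits and hospitalisations are an exploratory outcome, and utilisation feeds the cost-benefit analysis (Chapter 11), so uneven capture could reach those results too.

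Two different SAE clocks leave staff without a single rule to follow or be audited against.

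**Working it through.** The plan gives no hypoglycaemia rate or harms calculation to reproduce, so the check is mainly textual.

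**1. Is hypoglycaemia a data item?** In the available text the event appears three times:
- as a history item in the HbA1c paragraph of Chapter 5;
- as the PCP's reason for a regimen change (Chapter 8);
- in the glucose-tablet example (Chapter 8).

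It is absent from the other described measures, Table 2, the SAE examples in Chapter 9 and the analyses in Chapter 11. The PCP notice for low HbA1c in Chapter 5 is a laboratory trigger and records no hypoglycaemic event. The instrument forms and part of the text before Chapter 3 were not available, so item-level content could not be checked.

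**2. Does capture differ by arm?**

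| Source | PC-OT | EUC |
|---|---|---|
| 6-monthly EMR review, unmasked coordinator | yes | yes |
| Participant report at baseline, 6 and 12 months; outside-care question | yes | yes |
| Monthly MEMS visit and log | yes | yes |
| At least 4 interventionist–PCP exchanges in the EMR | yes | no |
| PCP posts health events for the interventionist | yes | no |
| Interventionist reads the EMR before each of 3 boosters | yes | no |

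Let *p* be an equal true risk in both arms, and *d1* and *d0* the probabilities that an event is recorded in PC-OT and EUC. The recorded risk ratio is then (*p* × *d1*)/(*p* × *d0*) = *d1*/*d0*. It is 1.0 if capture is equal and above 1.0 if capture is fuller in PC-OT. The documents give neither probability, so only the likely direction can be argued.

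**3. Can scheduled contacts meet a 48-hour clock that runs from occurrence?** Assume events are uniform in time and each contact acts as a look. The share of events in the 48 hours before a look is 2/interval in days, and the mean delay is interval/2.
- Every 6 months (182.5 days): 2/182.5 = 1.1%; mean delay 182.5/2 = about 91 days.
- Every month (365.25/12 = 30.4 days): 2/30.4 = 6.6%; mean delay 30.4/2 = about 15 days.

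Neither schedule can generally meet the occurrence version. A clock that starts at learning can be met under either.

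**4. What would a zero count mean?** With 50 per arm, 0 of 50 gives a one-sided 95% upper bound of 1 − 0.05^(1/50) = 5.8% for *recorded* events. If a fraction *d* of events is recorded, the bound on the true risk is 5.8%/*d*. With *d* unknown, a zero count gives no usable bound.

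**The case against.** The best defence is that the plan has more routes to an event than the 6-monthly review.

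- **Other sources exist.** Participant report, the outside-care question and MEMS logs that note hospitalisation all operate in both arms. A reader might infer that the EMR review is the only search for harms, and the documents do not support that. None of these routes, however, is described as asking about hypoglycaemia, and the logs serve to adjust adherence rates.
- **The 6-monthly review is not the stated SAE route.** It sits under Health Care Utilization. Chapter 9 has all staff trained in SAE procedures and the PI told at once. Staff are in the home monthly and for treatment sessions, and the coordinator opens the EMR monthly to check for dose changes. Reading the review interval as the plan's SAE detection lag is therefore unsupported. Still, the available text does not tell staff to ask about SAEs at these contacts.
- **Serious events are partly covered.** Hypoglycaemia leading to an ER visit or admission already counts as an SAE, and visits within the TJU system should reach its EMR in either arm. This narrows any capture gap for such events but does not cover milder episodes.
- **The bias would not flatter PC-OT.** Fuller capture there would overstate its harm. That is fair, but a comparison distorted in either direction is hard to use.
- **The two clocks may be only loose wording.** Section 1 cites the IRB's requirement and can be met. The two sections still differ on the same duty.

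**Conclusion.** The point holds as a gap worth closing, not as proof of biased or missed safety data. Three things rest on the text:
- hypoglycaemia is anticipated but not named as something to collect or analyse;
- the principal search is a 6-monthly record review by an unmasked coordinator, in a record to which PC-OT alone adds interventionist exchanges and posted health events;
- the two SAE clocks contradict each other, and scheduled contacts cannot generally meet the occurrence version (about 1% of events at a 6-monthly look and 7% at a monthly one, if event times are uniform).

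Fuller capture in PC-OT is a reasonable inference about direction. A reader might go on to attach a false risk ratio to it, but any such figure would rest on invented capture rates, and equal capture is not excluded. A reader might also assume that most hypoglycaemia stays out of the medical record; the documents say nothing on this, and the point does not need it. Finally, the claim is that hypoglycaemia is not named in the available text. The unseen forms may ask about it.

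**What to change.** Add two or three fixed questions to the research assistant's monthly MEMS visit, worded identically in both arms, on hypoglycaemia, ER visits and hospitalisation since the last visit. Send any answer that meets the SAE definition to SAE reporting, and add a table of these events by arm to Chapter 11. Reconcile sections 1 and 2 of Chapter 9 to a single SAE clock.

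The cost is slightly longer visits, which are already scheduled, and one extra table. Recall shortens from six months to one, and the questions are asked by someone not listed among the unmasked staff. The answers remain self-report, which Chapter 5 itself describes as affected by memory problems. Reporting may still differ by arm, because participants know their assignment and only PC-OT has Action Plans for glucose monitoring. The change makes capture more even; it does not guarantee that it is equal.
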